### 8.1.4 Safety Variables and Analysis

The safety variables are PTAEs, treatment emergent adverse events (TEAEs), application site adverse events, investigator and subject dermal tolerability assessments, physical examination, vital signs (blood pressure pulse rate, and oral temperature) and CTA.

All AEs will be coded from the verbatim text to the lower level term (LLT) and mapped to preferred term (PT) and primary system organ class (SOC) using the Medical Dictionary for

Allergan		06 Feb 2018
CMO-MA-MED-0530	Version 2	Page 40 of 59

Regulatory Activities (MedDRA). For PTAEs, the number and percentage of subjects reporting at least 1 PTAE will be tabulated by descending order of incidence rate, by primary SOC and PT, and by primary SOC, PT, and severity. TEAEs regardless of causality, application site AEs, and treatment-related TEAEs will be analyzed in the same manner. Maximum severity of each dermal tolerability measure over the treatment period will be summarized using a frequency distribution. The same analysis will be performed for at least a 1-grade worsening from baseline (ie, predose on day 1) over the treatment period for each tolerability measure.

Physical examination and vital signs data will be tabulated. Raw data and change from baseline in each vital sign measure will be summarized using descriptive statistics.

Clinician's Telangiectasia Assessment will be summarized using a frequency distribution by visit. More detailed analyses will be described in the analysis plan.

### 8.1.5 Interim Analyses

No interim analysis is planned for this study.

### 8.1.6 Handling of Missing Data

Missing data strategy will be documented in the statistical analysis plan.

#### 8.2 Determination of Sample Size

Sample size for this study was calculated using estimated incidence rate of treatment-related AEs for daily application of oxymetazoline HCl cream 1% in conjunction with energy-based therapy. A conservative estimate of the empirical incidence rate of study drug related adverse events ( $p_0$ ) was 8.2% (based on the oxymetazoline arm of 3 Allergan pivotal studies). In the scenario of improved overall efficacy outcomes resulting from the combination of oxymetazoline treatment with energy-based devices, a 14% increase (less than 15%) in the treatment-related adverse event rate may still be tolerable or warrant further clinical development. Thus, we choose to use  $\delta = 0.14$  as the margin of indifference.

Sample size calculation for this study is based on one proportion equivalence test for testing (2-sided) the null hypothesis  $H_0$ :  $|p - p_0| > \delta$  against the alternative hypothesis  $H_1$ :  $|p - p_0| < \delta$ . A sample size of N = 43 is required for attaining a power of 80% while controlling Type-I error rate of the test at 5%. To allow for a small percentage of potential subject withdrawal, approximately 45 subjects will be enrolled into this study.

#### 8.3 Protocol Deviations

Major protocol deviations may include, but are not limited to:

- Inclusion/Exclusion criteria violations.
- Inadequate compliance with study drug.
- Prohibited medications taken.
- Significant deviations from the study drug administration schedule.
- Other protocol deviations that could affect subjects' outcomes.

The final list of major protocol deviations will be defined during the data review meeting.

# 9 QUALITY ASSURANCE AND QUALITY CONTROL

#### 9.1 Audit and Inspection

Study centers and study documentation may be subject to Quality Assurance audit during the course of the study by the sponsor or its nominated representative. In addition, inspections may be conducted by regulatory authorities at their discretion.

#### 9.2 Monitoring

Data for each subject will be recorded on an eCRF. Data collection must be completed for each subject who signs an ICF and is administered study drug.

In accordance with current Good Clinical Practice (cGCP) and ICH guidelines, the study monitor will carry out source document verification at regular intervals to ensure that the data collected in the eCRF are accurate and reliable. Monitoring will be performed both on site and remotely, for further details, refer to the Monitoring Plan.

The investigator must permit the monitor, the IEC/IRB, the sponsor's internal auditors, and representatives from regulatory authorities direct access to all study-related documents and pertinent hospital or medical records for confirmation of data contained within the eCRFs.

# 9.3 Data Management and Coding

INC Research will be responsible for activities associated with the data management of this study. This will include setting up a relevant database and data transfer mechanisms, along with appropriate validation of data and resolution of queries. Data generated within this clinical study will be handled according to the relevant standard operating procedures (SOPs) of the data management and biostatistics departments of INC Research.

Study centers will enter data directly into an electronic data capture (EDC) system by completing the eCRF via a secure internet connection. Data entered into the eCRF must be verifiable against source documents at the study center. Data to be recorded directly on the eCRF will be identified and the eCRF will be considered the source document. Any changes to the data entered into the EDC system will be recorded in the audit trail and will be FDA Code of Federal Regulations (CFR) 21 Part 11 compliant.

Medical coding will use Medical Dictionary for Regulatory Activities (MedDRA) for concomitant diseases and AEs and WHODrug for medications.

Missing or inconsistent data will be queried in writing to the investigator for clarification. Subsequent modifications to the database will be documented.

# **10 RECORDS AND SUPPLIES**

#### **10.1 Drug Accountability**

On receipt of the study drug, the investigator (or deputy) will conduct an inventory of the supplies and verify that study drug supplies are received intact and in the correct amounts before completing a supplies receipt. The investigator will retain a copy of this receipt at the study center and return the original receipt to the study monitor. The monitor may check the study supplies at each study center at any time during the study.

It is the responsibility of the study monitor to ensure that the investigator (or deputy) has correctly documented the amount of the study drug received, dispensed, and returned on the dispensing log that will be provided. A full drug accountability log will be maintained at the study center at all times. The study monitor will arrange collection of unused study drug returned by the subject. The study monitor will also perform an inventory of study drug at the end of the study. Accountability may be performed remotely (refer to Monitoring Plan for further detail). All discrepancies must be accounted for and documented.

#### **10.2** Financing and Insurance

Financing and insurance of this study will be outlined in a separate agreement between INC Research and the sponsor.

# **11 ETHICS**

#### 11.1 Independent Ethics Committee or Institutional Review Board

Before initiation of the study at each study center, the protocol, the ICF, other written material given to the subjects, and any other relevant study documentation will be submitted to the appropriate IEC/IRB. Written approval of the study and all relevant study information must be obtained before the study center can be initiated or the study drug is released to the investigator. Any necessary extensions or renewals of IEC/IRB approval must be obtained for changes to the study such as amendments to the protocol, the ICF, or other study documentation. The written approval of the IEC/IRB together with the approved ICF must be filed in the study files.

The investigator will report promptly to the IEC/IRB any new information that may adversely affect the safety of the subjects or the conduct of the study. The investigator will submit written summaries of the study status to the IEC/IRB as required. On completion of the study, the IEC/IRB will be notified that the study has ended.

#### **11.2 Regulatory Authorities**

Relevant study documentation will be submitted to the regulatory authorities of the participating countries, according to local/national requirements, for review and approval before the beginning of the study. On completion of the study, the regulatory authorities will be notified that the study has ended.

#### 11.3 Ethical Conduct of the Study

The investigator(s) and all parties involved in this study should conduct the study in adherence to the ethical principles based on the Declaration of Helsinki, GCP, ICH guidelines, and the applicable national and local laws and regulatory requirements.

#### 11.4 Informed Consent

The process of obtaining informed consent must be in accordance with applicable regulatory requirement(s) and must adhere to GCP.

The investigator is responsible for ensuring that no subject undergoes any study-related examination or activity before that subject has given written informed consent to participate in the study.

The investigator or designated personnel will inform the subject of the objectives, methods, anticipated benefits, and potential risks and inconveniences of the study. The subject should be given every opportunity to ask for clarification of any points s/he does not understand and, if necessary, ask for more information. At the end of the interview, the subject will be given ample time to consider the study. Subjects will be required to sign and date the ICF. After signatures are obtained, the ICF will be kept and archived by the investigator in the investigator's study file. A signed and dated copy of the subject ICF will be provided to the subject.

Photographs of the subject's face will be taken as part of this study. If a subject does not consent to have the photographs taken, they cannot participate in the study. Subjects will also have the option of indicating whether or not they give permission for the use of their study photographs for advertising, publicity, and promotional purposes. If subjects do not consent to their photographs being used, they will be excluded from participating in the study.

Allergan		06 Feb 2018
CMO-MA-MED-0530	Version 2	Page 44 of 59

It should be emphasized that the subject may refuse to enter the study or to withdraw from the study at any time, without consequences for their further care or penalty or loss of benefits to which the subject is otherwise entitled. Subjects who refuse to give or who withdraw written informed consent should not be included or continue in the study.

If new information becomes available that may be relevant to the subject's willingness to continue participation in the study, a new ICF will be approved by the IEC(s)/IRB(s) (and regulatory authorities, if required). The study subjects will be informed about this new information and reconsent will be obtained.

# 11.5 Subject Confidentiality

Monitors, auditors, and other authorized agents of the sponsor and/or its designee, the IEC(s)/IRB(s) approving this research, and the US FDA, as well as that of any other applicable agency(ies), will be granted direct access to the study subjects' original medical records for verification of clinical study procedures and/or data, without violating the confidentiality of the subjects to the extent permitted by the law and regulations. In any presentations of the results of this study or in publications, the subjects' identity will remain confidential.

All personal data collected and processed for the purposes of this study should be managed by the investigator and his/her staff with adequate precautions to ensure confidentiality of those data, and in accordance with the Health Insurance Portability and Accountability Act, applicable to national and/or local laws and regulations on personal data protection.

# 12 REPORTING AND PUBLICATION, INCLUDING ARCHIVING

Essential documents are those documents that individually and collectively permit evaluation of the study and quality of the data produced. After completion of the study (end of study defined as the date of the last visit of the last subject), all documents and data relating to the study will be kept in an orderly manner by the investigator in a secure study file. This file will be available for inspection by the sponsor or its representatives. Essential documents should be retained for 2 years after the final marketing approval in an ICH region or for at least 2 years since the discontinuation of clinical development of the study drug. It is the responsibility of the sponsor to inform the study center when these documents no longer need to be retained. The investigator must contact the sponsor before destroying any study-related documentation. In addition, all subject medical records and other source documentation will be kept for the maximum time permitted by the hospital, institution, or medical practice.

The sponsor must review and approve any results of the study or abstracts for professional meetings prepared by the investigator(s). Published data must not compromise the objectives of the study. Data from individual study centers in multicenter studies must not be published separately.

# **14 APPENDICES**

14.1 Clinician Erythema Assessment Photonumeric Guide

# Clinician Erythema Assessment Scale with Photonumeric Guide

The Clinician Erythema Assessment (CEA) Scale with Photonumeric Guide is a tool used for the static assessment of overall facial erythema. The CEA scale uses a 5-point ordinal scale representing each grade of erythema from 0-4. Each grade includes a brief description of erythema, accompanied by representative frontal view photographs. This scale is a tool for the assessment of overall facial erythema based on appearance the day of evaluation, without relying on prior memory, perception or assessment of change as compared to previous assessments.

Using the CEA scale with photonumeric guide, the clinician should select one of the following CEA grades which best describes the severity of facial erythema:

Grade	Descriptions
0	Clear skin with no signs of erythema a
1	Almost clear of erythema, slight redness
2	Mild erythema, definite redness
3	Moderate erythema, marked redness
4	Severe erythema, fiery redness

a - Normal healthy skin color as seen in individuals without rosacea

In determining the appropriate CEA grade the clinician should evaluate the degree of facial erythema the patient presents with at the time of evaluation. If the patient has diffuse facial erythema the clinician should assign a CEA grade based on the overall facial erythema. If the patient has localized erythema the clinician should assign a CEA grade for the erythematous area of the face.

This photonumeric guide will serve as a tool to assist the clinician in assigning a CEA grade that is the best representation of facial erythema.

Version 2

06 Feb 2018 Page 50 of 59

Version 2

06 Feb 2018 Page 51 of 59

Version 2

06 Feb 2018 Page 52 of 59

Version 2

06 Feb 2018 Page 53 of 59

Version 2

06 Feb 2018 Page 54 of 59

# 14.2 Items From Satisfaction Assessment for Rosacea Facial Redness

# **INSTRUCTIONS**

This questionnaire includes two questions about how satisfied you are with the facial redness caused by your rosacea.

Before answering each question, please look in the mirror and think about the redness on your whole face caused by your rosacea. Please mark ONE "X" in the box ( $\square$ ) that best describes your satisfaction right now.

There are no right or wrong answers to any of the questions.

1. Right now, how satisfied are you with the appearance of your facial redness?

2. Right now, how satisfied are you with the amount of redness on your face?

# 14.3 FACE-QTM - Satisfaction With Skin

# FACE-Q™ - SATISFACTION WITH SKIN

For each question, circle only one answer. With your facial skin (complexion) in mind, in the past week, how satisfied or dissatisfied have you been with:

		Very Dissatisfied	Somewhat Dissatisfied	Somewhat Satisfied	Very Satisfied
a.	How your facial skin looks at the end of your day ?	1	2	3	4
b.	How healthy your facial skin looks?	1	2	3	4
с.	How attractive your facial skin makes you look?	1	2	3	4
d.	How smooth your facial skin looks?	1	2	3	4
e.	How clear your facial skin (complexion) looks?	1	2	3	4
f.	How refreshed your facial skin makes you look?	1	2	3	4
g.	How hydrated your facial skin looks?	1	2	3	4
h.	How your facial skin looks when you first wake up ?	1	2	3	4
i.	How radiant your facial skin looks?	1	2	3	4
j.	How the tone (color) of your facial skin looks?	1	2	3	4
k.	How your pores look?	1	2	3	4
I.	How even-colored your facial skin looks?	1	2	3	4

Copyright©2013 Memorial Sloan-Kettering Cancer Center, New York, USA. All rights reserved.

The FACE-Q, authored by Drs. Andrea Pusic, Anne Klassen and Stefan Cano, is the copyright of Memorial Sloan-Kettering Cancer Center (Copyright ©2013, Memorial Sloan-Kettering Cancer Center). The FACE-Q has been provided under license from Memorial Sloan-Kettering Cancer Center and must not be copied, distributed or used in any way without the prior written consent of Memorial Sloan-Kettering Cancer Center.

Note to Investigators: This scale can be used independently of the other scales. A REDCap Data Dictionary file is available (http://projectredcap.org/).

Psychometric Paper: Klassen AF, Cano SJ, Schwitzer J, Baker SB, Carruthers A, Carruthers J, Chapas A, Pusic AL. Development and Psychometric Validation of the FACE-Q Skin, Lips and Facial Rhytides Appearance Scales and Adverse Effect Checklists for Cosmetic Procedures. JAMA Dermatol. 2016 Apr 1;152(4):443-51.

# FACE-Q™ - SATISFACTION WITH SKIN CONVERSION TABLE

Instructions: Higher scores reflect a better outcome. If missing data is less than 50% of the scale's items, insert the mean of the completed items. Use the Conversion Table below to convert the raw scale summed score into a score from 0 (worst) to 100 (best).

SUM SCORE	E EQUIVALENT RASCH TRANSFORMED SCORE (0-100)	
12	0	
13	3	
14	9	
15	14	
16	18	
17	21	
18	24	
19	26	
20	29	
21	32	
22	34	
23	36	
24	39	
25	41	
26	43	
27	45	
28	47	
29	49	
30	51	
31	53	
32	55	
33	57	
34	59	
35	61	
36	63	
37	65	
38	67	
39	69	
40	72	
41	74	
42	76	
43	79	
44	81	
45	84	
46	88	
47	93	
48	100	

Allergan		06 Feb 2018
CMO-MA-MED-0530	Version 2	Page 59 of 59

The purpose of this statistical analysis plan (SAP) is to provide details of the statistical analyses and reporting that are outlined in the study protocol, which is dated on Oct 12, 2017 and titled "Multicenter, Open-Label, Interventional Study on the Safety and Tolerability of Oxymetazoline and Energy-Based Therapy in Subjects with Rosacea". This SAP should be reviewed in conjunction with the study protocol. Information contained in the protocol will not be restated unless it is essential for the descriptions in this SAP. In case of any discrepancies (for example, the definition of the Safety Analysis Population) between the protocol and the SAP, the SAP will supersede the protocol, as the SAP is intended to be more specific and precise with respect to statistical analysis and reporting. Any amendments to the SAP will be made prior to database lock. Any additional analyses not described in the final SAP or deviations from the final SAP will be documented in the clinical study report.

This study is a Phase 4 study sponsored by Allergan Plc. This study is a multicenter, interventional, open-label safety and tolerability study to evaluate the safety and tolerability of oxymetazoline HCl cream 1.0% when used as an adjunctive treatment to energy-based therapy for subjects with moderate to severe persistent facial erythema associated with rosacea.

Approximately 45 subjects will be enrolled into this study at 4 clinical sites in the United States. The duration of the study for each subject is 10 weeks. This includes a screening period of up to 2 weeks, a treatment period of 8 weeks, comprising of daily dosing of study drug and 2 energy-based therapy sessions, followed by a final exit visit at Week 8 (Day 56).

There will be no interim analysis. One final analysis is planned for this study. The final analysis will be performed at the completion of the study. Database lock will be executed for the final analysis.

1.1 Primary Study Objectives and Design

1.1.1 Study Design

This is a multicenter, interventional, single-arm, open-label safety and tolerability study.

Sample size calculation and power consideration are discussed in Section 8.2 of the study protocol. A total of 45 subjects with rosacea-associated moderate to severe persistent facial erythema will be enrolled into this study. Subjects will be screened for eligibility, and will be consented for the study entry.

On Day 1, all subjects will receive one of the following energy-based therapies: Potassium Titanyl Phosphate (KTP), Pulsed Dye Laser (PDL) or Intense Pulsed Light (IPL). After a 2-day washout, oxymetazoline HCl cream 1.0% will be applied once-daily starting from Day 3 up through Day 27. On Day 29, all subjects will receive a second energy-based therapy, followed by a 2-day washout and then once daily application of oxymetazoline HCl cream 1.0% up through Day 56.

1.1.2 Primary Objectives

The primary objective is to evaluate the safety and tolerability of oxymetazoline HCl cream 1.0% when used as an adjunctive treatment to energy-based therapy for subjects with moderate to severe persistent facial erythema associated with rosacea.

1.1.3 Secondary and Other Objectives

The secondary objective is to evaluate preliminary measures of efficacy of oxymetazoline HCl cream 1.0% when used as an adjunctive treatment to energy-based therapy for subjects with moderate to severe persistent facial erythema associated with rosacea.

2. Analysis Populations and Data Conventions

2.1 Analysis Populations

To adequately describe the appropriate statistical analyses, four analysis populations are defined as follows:

• Enrolled Population: consists of all subjects who signed an informed consent form (ICF), thus deemed as enrolled for the study.

• Safety Analysis Population: consists of all enrolled subjects who met the eligibility criteria and had an energy-based therapy and received at least one dose of study drug as treatment in this study.

• Evaluable Population: consists of all safety subjects who had at least one baseline efficacy assessments at Day 1 or prior to Day 1 and had at least one post-treatment efficacy assessments between Day 3 and Day 56, inclusive.

• Per Protocol Population: consists of all evaluable subjects who have not had any significant violations of the protocol, including but not limiting to significant deviations from the scheduled visit windows.

Unless specified otherwise, the enrolled population will be used for subject disposition, demographics, and baseline characteristics summaries; the safety analysis population will be used for safety analyses, and the evaluable population will be used for the efficacy analyses. Efficacy analyses may be repeated on the per protocol population if significant protocol violations are found prevalent in the evaluable population.

Note that in the context of this analysis plan (including the Table/Listing/Figure mockup shells), the terms safety analysis population and safety population are interchangeably used, and subjects in the safety population can be called safety subjects and subjects in the evaluable population can be called evaluable subjects.

2.2 Visit and Timepoint Windows

There is no plan to programmatically derive visit/timepoint windows. The scheduled visits/timepoints as recorded on the electronic Case Report Form (CRF) will be directly taken as the analysis visits/timepoints and will be used in reporting and analyses. The analysis visits include the Screening Visit, the Baseline (Day 1) Visit, the Day 3 Visit, the Day 29 Visit, the Day 31 Visit and the Day 56 (Exit Visit). The analysis timepoints corresponding to each visit on and after Day 1 include the Pre-Dose and the Post-Dose. Also refer to Table 1 Schedule of Assessments and Procedures (page 18) of the Protocol (Oct 12, 2017) for scheduled visits/timepoints.

If there are multiple observations of same assessment within the same scheduled visit/timepoint window, all values of multiple observations will be included for listing, but only the mean value of multiple observations will be used for the by-visit/timepoint summary or analysis. Assessment outside the scheduled visit/timepoint window will be marked as unscheduled assessment, and will be used for listing only.

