### Table 1 Schedule of Assessments and Procedures

\* Screening and baseline may occur on same day

a predose (Oxymetazoline HCl)/pretreatment (Energy-based therapy [KTP, PDL, or IPL])

b repeated only if screening/Day1 occur on separate days

c predose/pretreatment and 6 hr

d Study drug application only. No study drug will be dispensed

e predose/pretreatment and 1 hr

fpredose, 1 hr, 3 hr, and 6 hr

g 6 hr

h predose/pretreatment 1 hr and 6 hr

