### Pregnancy

Subjects who do not comply with the protocol, withdraw consent, or stop study drug for any other reason will not be replaced. Subjects are free to withdraw from the study at any time without providing reason(s) for withdrawal and without prejudice to further treatment. The reason(s) for withdrawal will be documented in the electronic case report form (eCRF).

Upon withdrawal from the study, any time after dosing has taken place, all efforts should be made to invite the subject to complete the early withdrawal visit. The same procedures should be performed as on the Day 56 (exit visit). The aim is to record data in the same way as for subjects who completed the study, particularly safety data.

Reasonable efforts will be made to contact subjects who are lost to follow-up. These efforts should be documented in the subject's file.

The sponsor has the right to terminate the study at any time in case of SAEs or if special circumstances concerning the study drug/energy therapy or the company itself occur, making further treatment of subjects impossible. In this event, the investigators will be informed of the reason for study termination.

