2.3.3 Study end date for patient

Study end date for each individual patient is defined as the date of completion of last assessment on the Day 56 visit or the date of the early withdrawal visit in case of earlier discontinuation from treatment. Note that subjects who are discontinued earlier from treatment for whatever reasons will be invited to attend the early withdrawal visit for the end-of-study data collection.

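### Worsening seen only at an unscheduled assessment is left out of the two primary any-timepoint tolerability endpoints

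*SAP*

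**What the plan says.** Protocol 5.1 lists three primary endpoints. Two are counts of subjects who worsen by one grade or more from baseline, in the Dermal Tolerability Assessment and in the CTA, at any timepoint in the treatment period. SAP 6.4 and 6.5 implement this by looking at the change from baseline at each timepoint and flagging a value of 1 or more. Both use as denominator the safety subjects with a baseline and at least one post-baseline value.

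SAP 2.2 takes visits and timepoints as recorded on the eCRF, without programmed windows, and sets two rules:

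- Out-of-window assessments: "Assessment outside the scheduled visit/timepoint window will be marked as unscheduled assessment, and will be used for listing only".
- Repeats within one visit and timepoint: "only the mean value of multiple observations will be used for the by-visit/timepoint summary or analysis".

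The analysis visits named in SAP 2.2 begin with Screening and end with "the Day 29 Visit, the Day 31 Visit and the Day 56 (Exit Visit". The early-withdrawal visit is not among them, although SAP 2.3.3 plans for it: "subjects who are discontinued earlier from treatment for whatever reasons will be invited to attend the early withdrawal visit for the end-of-study data collection". Protocol 5.5.4 says of that visit: "The aim is to record data in the same way as for subjects who completed the study, particularly safety data". Protocol 6.1.7 has it use the exit-visit procedures, and Protocol 8.1 describes it as the Day 56 exit visit.

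In Protocol Table 1, post-baseline CTA is scheduled on Days 3, 29, 31 and 56, always under the footnote "predose (Oxymetazoline HCl)/pretreatment (Energy-based therapy [KTP, PDL, or IPL".

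**The concern.** An endpoint worded as any timepoint promises that one bad grade, whenever recorded, makes the subject a case. The listing-only rule breaks that promise for the grades most likely to be taken because something was wrong, such as an extra check between visits. The subject is not set aside as missing; he or she is normally reported as not worsened. The error therefore runs in one direction, toward good tolerability, in a single-arm study whose primary aim is tolerability.

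The CTA flag also splits a demographic table (SAP 4.1), so a misclassified subject would appear in the wrong column there. Protocol 8.1.4 plans a maximum-severity summary for each dermal measure, but SAP 6.4 does not carry it over, so no table described in the SAP would show the loss.

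**Working it through.** **Denominators.** The plan gives no expected rate for either worsening endpoint. The only usable sizes are 43 required and about 45 enrolled, from Protocol 8.2. The 43 can be reproduced with p0 = 0.082 and margin 0.14. The lower limit, 0.082 − 0.14 = −0.058, is below zero, so only the upper limit, 0.222, can bind. With a one-sided 5% test and 80% power, n = [(1.645 × √(0.222 × 0.778) + 0.842 × √(0.082 × 0.918)) / 0.14]² = 42.7, rounded up to 43. That calculation concerns treatment-related adverse events and serves here only to supply N.

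**The chain of rules.**
1. The endpoint counts a worsening at any timepoint (Protocol 5.1).
2. Worsening is judged timepoint by timepoint (SAP 6.4, 6.5).
3. A value marked unscheduled goes to listings only (SAP 2.2), so it supplies no timepoint to step 2.
4. One other post-baseline value is enough for the denominator (SAP 6.4, 6.5).

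A subject whose only worsening sits in step 3 is therefore a non-case in the denominator.

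**Effect on the rate.** With m such subjects, the reported proportion is too low by m/N. The documents give no value for m, so the following values are assumptions:

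| m | N = 45 | N = 43 |
|---|---|---|
| 0 | 0 | 0 |
| 1 | 1/45 = 2.2 points | 1/43 = 2.3 points |
| 2 | 2/45 = 4.4 points | 2/43 = 4.7 points |

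If the subject has no other post-baseline value and so leaves the denominator too, the rate still cannot rise. With k counted cases, (k+1)/N − k/(N−1) = (N−1−k)/[N(N−1)], which is never negative.

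**Early withdrawal.** The Day 29 window is ±3 days (Days 26 to 32) and the Day 56 window is ±3 days (Days 53 to 59). A withdrawal visit on, say, Day 20 lies in neither. For CTA, the only scheduled post-baseline grade before it is Day 3, taken before the first application of cream. That grade alone keeps the subject in the denominator. The withdrawal-visit grade is the only one taken after study drug began, and whether it counts depends on how the eCRF labels the visit.

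**Repeats (conditional).** The next table applies only if the mean rule also feeds the any-timepoint classification, which SAP 2.2 does not state.

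| Baseline | Repeats | Change in mean | Counted by mean | Counted by worst grade |
|---|---|---|---|---|
| 0 | 1, 0 | 0.5 | no | yes |
| 1 | 2, 1 | 0.5 | no | yes |
| 0 | 1, 1, 0 | 0.67 | no | yes |
| 0 | 2, 0 | 1.0 | yes | yes |

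A grade of 0.5 also fits poorly with SAP 2.3.5, which treats ordinal variables as categorical.

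**The case against.** The case for leaving the plan alone has real weight.

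- Classifying at any timepoint already takes the worst grade across scheduled readings. This stands: a reader might infer that the SAP has no worst-grade logic at all, and that would be wrong. The gap is confined to unscheduled grades and, possibly, repeats.
- A reader might infer that early-withdrawal data are excluded. No passage says so. Protocol 5.5.4, 6.1.7 and 8.1 point toward recording that visit as the exit visit, which is a named analysis visit. What remains is that the SAP does not write the mapping down.
- A reader might infer that the 1 h and 6 h dermal readings are averaged, because SAP 2.2 says "The analysis timepoints corresponding to each visit on and after Day 1 include the Pre-Dose and the Post-Dose". The documents do not support this. The same section takes eCRF timepoints directly and refers to Table 1, whose footnote reads "predose/pretreatment 1 hr and 6 hr". The verb does not make the list exhaustive, and CTA has no post-dose reading. At most the wording needs tidying.
- The mean rule is worded for by-visit/timepoint output, and SAP 6.4 and 6.5 present the any-timepoint proportion separately from the by-visit one. That stands, so the repeats point is only conditional.
- Late readings entered under a scheduled eCRF label probably still count, since no windows are programmed. They are not part of this point.
- Restricting the count to scheduled readings gives every subject the same opportunities to be a case. This is the best argument for the rule, and it is met by reporting both proportions.
- A clinically significant worsening between visits may be reported as an adverse event. That helps, but Protocol 7.1.2.1 does not require every one-grade change to be reported as one.

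**Conclusion.** The point holds for out-of-window assessments: the SAP states a rule that conflicts with the any-timepoint wording of two primary endpoints, and its effect can only favour the product. The size is 2.2 points per affected subject at N = 45 (2.3 at N = 43). This assumes that the subject shows no worsening at any counted timepoint and has another post-baseline value. The number of such subjects cannot be derived from the documents and may be nil.

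The early-withdrawal point is an ambiguity rather than a stated exclusion, and it matters most for CTA. The repeats point depends on a reading that the SAP does not settle.

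The consequence is limited. Neither endpoint has a hypothesis test, a confidence interval or a decision threshold, and the values are listed. It is a worthwhile minor correction.

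**What to change.** In SAP 2.2, 6.4 and 6.5:

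- Derive any-timepoint worsening in dermal tolerability and CTA from the worst post-baseline grade over all recorded assessments: scheduled, repeat, unscheduled and early withdrawal.
- State that the mean-of-repeats rule does not apply to these two endpoints.
- Name the analysis visit to which the early-withdrawal visit belongs.
- Keep the by-visit tables on scheduled visits, and show the scheduled-only proportion beside the all-assessments one.
- Optionally, replace the Post-Dose label with the Table 1 timepoints.

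The cost is a few sentences and one derivation on data already collected and listed; the SAP's introduction allows amendments before database lock. The reported rates may be slightly less favourable. Subjects seen more often, possibly because of symptoms, have more chances to count. Showing the two proportions together lets the reader judge how much that matters.
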